#### 4.1 Populations Analysed

##### *Main study phase*

The primary efficacy analysis will be performed on the mITT population. Supportive analysis of the primary efficacy endpoints will be based on the ITT and the PP populations.

The secondary efficacy analyses will be based on the mITT population. Supportive analysis of the secondary analyses may be performed on the PP population.

The analyses of safety data will be performed based on the Safety population.

The analyses of PK data will be performed based on the PK population.

##### *Extension phase*

The analysis sets for the efficacy endpoints will be the ITT set and the PP set. Analyses and summary tables for the safety endpoints will be based upon the Safety population.

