- Change in pubertal stage using the Tanner method (genital stage in boys, breast stage in girls and pubic hair stage in both sexes) at Month 6 compared to baseline
- Proportion of children with stabilised pubertal stage compared to baseline stage using the Tanner method at Month 6
- Change in auxological parameters including height, growth velocity, weight and BMI at Month 3 and Month 6 compared to baseline
- Change in BA, difference between BA and CA at Month 6 compared to baseline
- Change in uterine length in girls and testicular volume in boys at Month 6 compared to baseline.

Safety:

- Incidence of treatment-emergent adverse events (TEAEs) throughout the study, including local tolerability
- Change in clinical safety laboratory (blood biochemistry, haematology and urinalysis) parameters at Month 3 and 6
- Change in physical examination and vital signs (blood pressure and heart rate) measurements at each visit.

Pharmacokinetics:***Exploratory Endpoint:***

- To assess sparse plasma triptorelin concentrations at Day 1, Month 3 and Month 6.

Extension phase:

For subjects participating into the extension study following endpoints will be analysed:

Efficacy:

- Proportion of children with LH suppression (defined as LH ≤ 3 IU/L) at Month 12
- Change in basal serum LH and FSH levels at Month 9 and Month 12
- Proportion of children with pre-pubertal levels of sex steroids (defined as oestradiol ≤ 20 pg/mL in girls and testosterone ≤ 0.3 ng/mL in boys) at Month 9 and Month 12
- Change in oestradiol levels in girls and testosterone levels in boys at Month 9 and Month 12
- Change in pubertal stage using the Tanner method (genital stage in boys, breast stage in girls and pubic hair stage in both sexes) at Month 12
- Proportion of children with stabilised pubertal stage compared to baseline stage using the Tanner method at Month 12
- Change in auxological parameters including height, growth velocity, weight and BMI at Month 9 and Month 12

- Change in BA, difference between BA and CA at Month 12
- Change in uterine length in girls and testicular volume in boys at Month 12

Safety:

- Incidence of treatment-emergent adverse events (TEAEs) throughout the study, including local tolerability
- Change in clinical safety laboratory (blood biochemistry, haematology and urinalysis) parameters at Months 9 and 12
- Change in physical examination and vital signs (blood pressure and heart rate) measurements at each visit.

Statistical Methods:***Main study phase:***

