***Extension phase:***

The extension of the study will provide the possibility for subjects to continue with their study drug treatment, per investigators decision, for an additional 6 months. This will imply a triptorelin injection at Month 6 and an additional triptorelin injection at Month 9, before they attend the End of Extension Phase (EOEP) visit at Month 12. This Extension phase is optional.

Each participant may be treated with the study drug for up to 12 months.

The Extension study design is described in the following study flow chart.

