***Extension phase:***

The number of participants included in the extension study will be dependent on the number of participants from study D-CN-52014-243 who give consent to continue into the extension study. A maximum of 32 participants will be expected to be enrolled in the extension phase.

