**4 ANALYSIS POPULATIONS (SETS)**

The following populations will be used during statistical analyses:

- **Screened population:** All participants screened (i.e. who signed the informed consent)
- **Safety population:** All participants who received at least one dose of study medication and have at least one post-baseline safety assessment
- **Intention-To-Treat population (ITT):** All participants who received at least one dose of study medication
- **Modified Intention-To-Treat population (mITT):** All treated participants having at least one baseline and at Month 3 post-baseline assessment of the primary efficacy endpoint

- **Per protocol set (PPS):** All participants in the mITT after exclusion of the participants who had major protocol deviations that could potentially affect the primary efficacy endpoint outcome for the participants
- **PK set (PKS):** All participants who received at least one dose of study medication and have at least one valid and quantifiable concentration in main study phase.

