#### **5.9 *Efficacy and Safety Evaluations (Extension Phase)***

An additional analysis on efficacy and safety endpoints will be performed considering the extension phase duration, a period of an additional 6 months, lasting until the End of Extension Phase Visit at Month 12.

As this is an extension phase following the main study phase, the efficacy and safety endpoints in the extension phase will be summarised descriptively. No formal statistical hypotheses testing will be performed.

Statistical analyses will include the following:

- For the continuous endpoints, the descriptive summary statistics (number of participants (n), mean, SD, median, minimum, maximum) will be calculated
- For the categorical endpoints, the summary statistics of number and percentage of participants and the exact two-sided 90% confidence interval (CI) will be calculated.

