### 5.9.2 Safety Endpoint for Extension Phase

The extension phase safety endpoints are the following;

- Incidence of treatment-emergent adverse events (TEAEs) throughout the study, including local tolerability
- Change in clinical safety laboratory (blood biochemistry, haematology and urinalysis) parameters at Months 9 and 12
- Change in physical examination and vital signs (blood pressure and heart rate) measurements at each visit

Unless otherwise specified, all the analysis of extension phase safety endpoints including AE, laboratory, physical examination and vital signs will be the same as main study phase.

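### Extension safety tables are assigned to a Safety population that does not require extension entry; read literally, extension-only adverse event percentages come out too low

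*SAP*

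**What the plan says.** SAP 4 defines the Safety population once: "All participants who received at least one dose of study medication and have at least one post-baseline safety assessment". The PK set in the same list is confined to the main study phase, but the Safety definition names no phase. For the extension, SAP 4.1 then states: "Analyses and summary tables for the safety endpoints will be based upon the Safety population". Protocol 11.1.1 gives the same rule. Neither document defines an extension safety set.

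On entry, SAP 2.2 says "This Extension phase is optional". Protocol 4.3 requires a specific consent, continuing benefit and no unacceptable safety issue. The only number is in SAP 2.3: "A maximum of 32 participants will be expected to be enrolled in the extension phase".

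On method, SAP 5.9 says "An additional analysis on efficacy and safety endpoints will be performed considering the extension phase duration". Subject to any stated exception, SAP 5.9.2 carries the main-phase method over: "all the analysis of extension phase safety endpoints including AE, laboratory, physical examination and vital signs will be the same as main study phase". With adverse events, the main-phase method in SAP 5.8.3 is the number and percentage of participants. The first extension safety endpoint in SAP 5.9.2 reads: "Incidence of treatment-emergent adverse events (TEAEs) throughout the study, including local tolerability".

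The Protocol synopsis (criteria for evaluation, extension phase) introduces both the efficacy and the safety endpoints with: "For subjects participating into the extension study following endpoints will be analysed".

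**The concern.** A percentage for the extension period should be divided by the children who were treated and followed in that period. Protocol 8.1 and 11.4.6 collect adverse events to the end-of-study visit at Month 6, and on to Month 12 only for children in the extension. A child who does not enter receives no third or fourth injection and has no scheduled adverse event collection after Month 6, yet belongs to the Safety population.

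Describing long-term safety is a stated extension objective (SAP 2.1.2). If non-entrants are counted in the denominator, the error has one direction: the extension looks safer than the main phase even when the risk among treated children is the same.

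**Working it through.** **1. Who is in the Safety population.** Local tolerability is assessed at injection and 2 hours later on Day 1 (Protocol Table 1 and 8.4). Almost every treated child therefore has a post-baseline safety assessment, and the set is close to all treated children, entrants or not.

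**2. The plan's own figure.** The documents give no extension denominator and no adverse event rate. The only relevant number is planned enrolment, and it reproduces. With n = 28 and success at 24 or more responders, the exact one-sided alpha at 70% is 0.0474 and the power at 90% is 0.858. Then 28 / 0.9 = 31.1, rounded up to 32.

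**3. Formula.** Let m be the number of entrants, S the Safety population and x the number of entrants with an event that starts in the extension.

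- Entrants only: x / m
- Literal rule: x / S = (x / m) × (m / S)
- Relative error: m / S − 1

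**4. Results.** Assume S = 32, that is, all enrolled children are treated and assessed. The documents do not give m, so a range is shown.

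| Entrants m | Factor m/32 | Relative error |
|---|---|---|
| 32 | 1.000 | 0% |
| 29 | 0.906 | −9.4% |
| 24 | 0.750 | −25% |
| 16 | 0.500 | −50% |

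**5. Effect on the SAP's own cut-offs.** SAP 5.8.3 asks for a row for non-serious TEAEs above 10% and a table of events reported in more than 5%.

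- Three children with an event among 24 entrants: 3/24 = 12.5% (exact 90% CI 3.5 to 29.2). The literal rule shows 3/32 = 9.4% (2.6 to 22.5), below the 10% row.
- One child among 16 entrants: 1/16 = 6.3%. The literal rule shows 1/32 = 3.1%, outside the 5% table.

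**6. What is not diluted.** Laboratory shift tables use children with both a baseline and a post-baseline value at the timepoint (SAP 5.8.4). Summaries of change from baseline use the number of observations (SAP 5.1.2). Non-entrants have no Month 9 or Month 12 values and drop out of both.

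**7. The numerator.** SAP 5.8.3 accepts an event as treatment-emergent by start date only up to the end-of-study visit or 185 days after the first dose, whichever comes first. SAP 5.9.2 carries this over without change. The end-of-study visit is at Day 182 (±3) and is also the first extension visit (Protocol 5.2.4). The extension ends at Day 365, so about 365 − 182 = 183 days lie outside the window. New events in that time would not qualify by start date. Only the rules on worsening grade and on causality changing to related, which have no end date, would still apply.

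**The case against.** The strongest reply is that the Protocol already gives the right denominator. Its synopsis limits the extension endpoints, safety included, to participating children, and SAP 2.6 declares no change from the protocol's statistical section. The SAP also applies another set by phase: participation duration in 5.2 is reported on the ITT population separately for each phase. Protocol Table 2 labels Month 6 as the extension baseline, so a programmer might apply the Safety population within phase. This shows what was probably intended, but it does not settle the rule. Protocol 11.1.1 repeats the unrestricted set, SAP 5.1.3 places baseline before the first injection of the study unless otherwise specified, and Appendix A3 says only that percentages use n. The result is a conflict between passages.

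Second, the endpoint wording extends over the whole study and can be read as cumulative incidence from Day 1, for which the full Safety population is correct. That stands for a cumulative table. The extension analysis is, however, framed around the additional 6 months, and SAP 5.8.3 counts a TEAE only where it started. Both favour extension-only counts.

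Third, the consequence is limited. The extension analysis is descriptive, counts are shown, and the disposition table in SAP 5.2 gives the number treated in the extension, so a reader could recalculate. That is fair, but a planned table should not need it. Protocol 8.1.5 also requires suspected related events to be reported after study completion. It is therefore too strong to say that nothing could ever be recorded for a non-entrant; what is missing is scheduled collection.

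Fourth, the TEAE window stands in a section headed as main phase and may have been meant for that phase alone. SAP 5.9.2 nevertheless adopts the main-phase analysis and states no other window.

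**Conclusion.** The point holds as a conflict over the denominator, with a literal reading that understates extension-only adverse event and local-tolerability percentages. With 32 in the Safety population, the relative shortfall runs from nil (all enter) through 9.4% (29 enter) and 25% (24 enter) to 50% (16 enter). These entry numbers are assumptions. The carried-over TEAE window would also remove new extension events from the numerator, an error in the same direction.

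A reader might infer more than the documents support:

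- **That the dilution is certain.** The synopsis points the other way, and there is no dilution if every child enters.
- **That a main-study set is being misapplied.** The Safety population is study-wide.
- **That the planned 10% dropout predicts about 29 entrants.** That allowance belongs to the Month 3 sample size and says nothing about entry to an optional extension.
- **That all extension safety tables are affected.** Laboratory shift tables and change summaries are not diluted in this way.

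**What to change.** In SAP 4, 4.1 and 5.9.2, and in Protocol 11.1.1:

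1. Define an Extension Safety set: all participants who received at least one extension injection (Month 6 or Month 9).
2. Use it as the denominator for extension-only adverse event and local-tolerability tables.
3. Label each TEAE table as extension-only or cumulative. Keep the full Safety population for the main phase and for any cumulative Day 1 to Month 12 table.
4. In SAP 5.8.3 or 5.9.2, give the TEAE start-date rule an extension window that runs to the end of the extension phase, so that new extension events are counted.

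The cost is a few sentences, one population flag and a revised TEAE derivation; no new data are needed. The downside for the sponsor is that extension adverse event percentages become higher wherever some children do not enter.

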### 5 STATISTICAL METHODS/ANALYSES

The statistical analyses will be performed in accordance with ICH E9 guideline and guidelines presented in section 8.

TigerMed will perform the statistical analysis of this study under the supervision of the Biometry department of IPSEN.

#### 5.1 General Considerations

The precision of the measurement for each continuous variable will be used to determine the number of decimal places to present in tables, figures, and derived listings. Unless otherwise specified, min and max values will be reported with the same decimal as the units of measure; the mean, median and SD will be reported to 1 greater decimal place, all of them will not be greater than 4 decimal places. Any values that require transformation to standard units (metric or International System [SI]) will be converted with the appropriate corresponding precision.

Percentages of categorical variables will be presented to 1 decimal place unless otherwise specified.

For laboratory values data below the lower limit of quantification (LLOQ) like “<xxx” or “<=xxx”, or above the upper limit of quantification (ULOQ) like “>xxx” or “>=xxx”, LLOQ or ULOQ (xxx) will be used for calculation of descriptive statistics. The original laboratory values (“<xxx”, “<=xxx”, “>xxx” or “>=xxx”) are presented in the listings.

All statistical analyses will be performed using the SAS® software version 9.4 or above version.

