5.3 Laboratory Assessments

All efficacy parameters listed below (i.e. LH, FSH, testosterone and oestradiol), and samples for triptorelin PK, will be analysed centrally. The preparation and storage of samples are described separately in the Laboratory Manual. Laboratory safety tests will be conducted locally.

At Day 1 visit, in case of abnormal blood glucose as per Investigator's judgement, repetition of this test will be performed before the first triptorelin injection.

The following laboratory parameters will be analysed from samples collected at timepoints described in [Table 1](#):

- (1) LH and FSH concentrations at baseline and after GnRH stimulation (this analysis will be conducted as described in the Laboratory Manual);
- (2) Oestradiol and testosterone levels;
- (3) Pregnancy test (only in female participants with childbearing potential), [Section 8.1.6](#);
- (4) Haematology (complete blood count (CBC)), [Section 8.2.1](#);
- (5) Blood chemistry such as creatinine and glucose, [Section 8.2.2](#);
- (6) Liver function tests, including ALT, AST, alkaline phosphatase (ALP) and bilirubin, [Section 8.2.2](#);
- (7) Urinalysis (pH, protein, ketones, bilirubin, blood, urobilinogen, nitrites, leukocytes, glucose and specific gravity by dipstick), [Section 8.2.3](#);
- (8) Pharmacokinetic concentrations, [Section 9.1](#).

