11.4.4.2 Secondary Efficacy Endpoint

As indicated in Section 7.2, the secondary efficacy endpoints are the following:

- Change in basal serum LH and FSH levels at Month 3 and Month 6 compared to baseline
- Proportion of children with LH suppression defined as stimulated peak LH ≤ 3 IU/L after GnRH stimulation at Month 6
- Change in peak LH level after the GnRH stimulation test at Month 3 and Month 6 compared to baseline
- Change in peak FSH level after the GnRH stimulation test at Month 3 and Month 6 compared to baseline
- Proportion of children with pre-pubertal levels of sex steroids (defined as oestradiol ≤ 20 pg/mL in girls and testosterone ≤ 0.3 ng/mL in boys) at Month 3 and Month 6
- Change in oestradiol levels in girls and testosterone levels in boys at Month 3 and Month 6 compared to baseline
- Change in pubertal stage using the Tanner method (genital stage in boys, breast stage in girls and pubic hair stage in both sexes) at Month 6 compared to baseline
- Proportion of children with stabilised pubertal stage compared to baseline stage using the Tanner method at Month 6
- Change in auxological parameters including height, growth velocity, weight and BMI at Month 3 and Month 6 compared to baseline
- Change in BA, difference between BA and CA at Month 6 compared to baseline
- Change in uterine length in girls and testicular volume in boys at Month 6 compared to baseline.

11.4.4.3 *Exploratory Pharmacokinetics Endpoint*

- To assess sparse plasma triptorelin concentrations at Day 1, Month 3 and Month 6.

11.4.5 *Adjustment for Country/Centre Effect*

Descriptive analysis will be carried out to evaluate any possible centre effect.

11.4.6 *Safety Evaluation (Main Phase)*

Safety endpoints are indicated in Section 3.2.3.

All safety data will be included in the participant data listings. Analyses and summary tables will be based on the Safety population.

All AEs will be coded according to the Medical Dictionary for Regulatory Activities (MedDRA) version (version in use before database lock) and will be classified by MedDRA preferred term (PT) and system organ class (SOC). All AE listings will be presented by participant and by SOC and PT.

The incidence of all reported TEAEs, TEAEs associated with early withdrawal and SAEs will be tabulated overall. In addition, summary tables will be presented by maximum intensity and drug relationship.

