**Table 1 Secondary Efficacy Endpoints and Evaluations**

Measure	Timepoint	Variable	Endpoint
Basal LH and FSH	Baseline, Month 3 and Month 6 (EOS)	LH and FSH concentration	Change in basal serum LH and FSH levels at Month 3 and Month 6 compared to baseline
Peak LH after GnRH	Baseline, Month 3 and	Peak LH levels after	Change in peak LH levels after GnRH stimulation test at

stimulation test	Month 6 (EOS)	GnRH stimulation (30, 60 and 90 minutes)	Month 3 and Month 6 compared to baseline; Proportion of children with LH suppression defined as stimulated peak LH $\leq 3$ IU/L after GnRH stimulation at Month 6.
Peak FSH levels after GnRH stimulation test	Baseline, Month 3 and Month 6 (EOS)	Peak FSH levels after GnRH stimulation (30, 60 and 90 minutes)	Change in peak FSH levels after GnRH stimulation test at Month 3 and Month 6 compared to baseline.
E2 and testosterone serum concentrations	Baseline, Month 3 and Month 6 (EOS)	Sex steroids levels	Proportion of children with sex steroids suppressed within prepubertal ranges (E2 $\leq 20$ pg/mL in girls and testosterone $\leq 0.3$ ng/mL in boys); Change in sex steroids levels compared to baseline
Pubertal stage (Tanner Method)	Baseline, Month 6 (EOS)	Pubertal stage	Change in pubertal stage (genital stage in boys, breast stage in girls and pubic hair stage in both sexes) compared to baseline; Proportion of children with stabilised pubertal stage compared to baseline
Auxological parameters (height, growth velocity, weight, BMI)	Baseline, Month 3 and Month 6 (EOS)	-	Change in auxological parameters compared to baseline
BA	Baseline, Month 6 (EOS)	-	Change in BA, difference between BA and CA compared to baseline
Uterine/ovary or testis volume	Baseline, Month 6 (EOS)	Gonad development	Change in uterine length in girls and testicular volume in boys compared to baseline

BA = Bone age; BMI = Body mass index; CA = Chronological age; E2 = Oestradiol; EOS = End of Study; FSH = Follicle-stimulating hormone; GnRH = Gonadotropin-releasing hormone; LH = Luteinising hormone.

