### 5.7.3.2 *Secondary Analysis*

For secondary efficacy endpoints related to a change at Month 3, 6 compared to baseline, the descriptive summary statistics (number of participants (n), mean, SD, median, quartiles, minimum, maximum) will be calculated on the mITT.

Exact two-sided 90% CI will also be constructed for all secondary endpoints expressed as proportions.

GV cm/y, Height, Weight, BMI, FSH, LH values, Bone age, difference between Chronological age and Bone age, mean Oestradiol/Testosterone, Uterine Length and Testicular Volume over time will be graphically presented via individual observed values (scatter) as well as mean and standard deviation of the observed values (Baseline, Month 3, and Month 6).

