### **7 DERIVED DATA (IF APPLICABLE)**

When applicable, below derivation rules should be followed:

- Change from baseline**

Change from baseline at a given visit will be calculated as a difference from baseline.

- Age**

Age (years) will be calculated as follows and truncated to the largest integer that is less than or equal to the calculated result:

Age = (informed consent date of main study phase - birth date + 1)/365.25.

- **Chronological Age**

Chronological Age (years) will be calculated as follows and truncated to the largest integer that is less than or equal to the calculated result:

Chronological Age = (Visit Date - birth date + 1)/365.25.

- **BMI**

BMI (kg/m^2) will be derived as Weight (kg)/[Height(cm)/100]\*\*2 measured at each visit and rounded to the nearest decimal.

- **Bone Age**

For bone age recorded as 9+ or 10-, the original result will be listed in listing and update 9+ to 9.25 and 10- to 9.75 in the summary analysis.

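### Setting hormone results below the assay limit equal to that limit raises on-treatment means and tends to understate the mean fall in basal LH, basal FSH, oestradiol and testosterone

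*SAP*

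**What the plan says.** SAP 5.1 covers laboratory values generally: for results reported as below or above the assay range, "LLOQ or ULOQ (xxx) will be used for calculation of descriptive statistics". The original censored text is kept for the listings. The history of changes shows that this rule came in with SAP version 2.1.

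Protocol 5.3 lists "LH and FSH concentrations at baseline and after GnRH stimulation" among the laboratory parameters, together with oestradiol and testosterone. The SAP gives no separate rule for these hormones. Section 5.10 has a different rule, but only for triptorelin concentrations.

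The affected secondary endpoints (Protocol 11.4.4.2) are "Change in basal serum LH and FSH levels at Month 3 and Month 6 compared to baseline" and "Change in oestradiol levels in girls and testosterone levels in boys at Month 3 and Month 6 compared to baseline". SAP 7 defines the derivation: "Change from baseline at a given visit will be calculated as a difference from baseline". SAP 5.7.3.2 then states that "the descriptive summary statistics (number of participants (n), mean, SD, median, quartiles, minimum, maximum) will be calculated on the mITT", and plans plots of individual values and of mean and SD over time. SAP 5.9.1 carries the same methods into the extension phase. Neither document gives an LLOQ for any hormone or plans a count of results below it.

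**The concern.** A result below the LLOQ lies somewhere between 0 and the LLOQ. The rule always picks the top of that interval. Treatment aims to push these hormones down, so censored results are likely to be more common at Months 3 and 6 than at baseline, and the substitution then acts mainly on one side of the subtraction.

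The tabulated mean change would depend partly on the laboratory's assay limit: the same children measured with a less sensitive assay would show a smaller fall. A child below the limit at both visits would contribute a 0 that looks like a measured absence of change. The tables would not let a reader see how often either happens. Protocol 11.3 makes the descriptive results the reference for judging similarity with the overseas population, so these summaries carry some weight even though nothing is tested.

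**Working it through.** The plan gives no figure on this point, so there is none to reproduce.

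**1. What follows from the rule alone.** With lower limit L, the analysed value is g(x) = max(x, L).

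- g(x) ≥ x, so every visit mean is too high or unchanged.
- g never widens the distance between two values. Visit-level SDs are therefore too small or unchanged, and no child's absolute change can grow.
- If both values are below L, the analysed change is L − L = 0.
- Error in mean change = f_post × (L − mean of censored on-treatment values) − f_base × (L − mean of censored baseline values), where f is the share below L. The error is at most f_post × L. It is positive, so the fall is understated, when the first term is the larger.

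**2. Which endpoints are exposed.** Eligibility (Protocol 4.1) requires a stimulated peak LH of at least 5 IU/L. With any LLOQ below 5, the change in peak LH cannot be an artificial 0. Under the levels tried for the check, its mean change moved by about 0%. No entry minimum protects basal LH, basal FSH, oestradiol or testosterone.

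**3. Size for oestradiol (all inputs assumed).** Lognormal, log-SD s = 0.7, medians m of 20 pg/mL at baseline and 5 pg/mL on treatment. With M = m × exp(s²/2) and z = ln(L/m)/s, the mean after substitution is M × [1 − Φ(z − s)] + L × Φ(z).

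- True means: 20 × 1.2776 = 25.55 and 5 × 1.2776 = 6.39. True mean change: −19.16.
- L = 10, baseline: z = −0.990, so 25.55 × (1 − 0.0455) + 10 × 0.161 = 26.00.
- L = 10, on treatment: z = 0.990, so 6.39 × (1 − 0.614) + 10 × 0.839 = 10.85.
- Reported change: 10.85 − 26.00 = −15.15, an understatement of 4.01/19.16 = 21%.

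| LLOQ (pg/mL) | Below LLOQ, baseline / on treatment | Mean change (true −19.16) | On-treatment SD (true 5.08) | Median change (true about −14.2) | Exact zeros |
|---|---|---|---|---|---|
| 2 | 0.1% / 9.5% | −19.12 | 5.03 | −14.1 | 0% |
| 5 | 2.4% / 50% | −18.24 | 4.45 | −13.1 | 1% |
| 10 | 16% / 84% | −15.15 | 3.16 | −9.4 | 13–14% |
| 20 | 50% / 98% | −9.21 | 1.61 | 0.0 | 49% |

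Median change comes from 400,000 simulated pairs. The last two columns take baseline and on-treatment values as independent within a child. With correlation 0.8, exact zeros at LLOQ 10 are about 16%.

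**4. Other assumed levels.** Oestradiol medians of 15 to 6 pg/mL (log-SDs 0.8 and 0.6): mean fall understated by 3.5%, 19.6% and about 52% at LLOQ 5, 10 and 20. Basal LH medians of 0.8 to 0.3 IU/L (log-SDs 1.0 and 0.6): 0%, 0.9% and about 3.5% at LLOQ 0.1, 0.2 and 0.3, with 0.1% to 16% exact zeros depending on LLOQ and correlation. Basal FSH and testosterone were not simulated.

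**5. SD of the change score.** Same oestradiol case as step 3, LLOQ 10: it goes from about 21.0 to 20.2 with correlation 0, from 18.5 to 19.0 with 0.5, and from 16.7 to 18.1 with 0.8. The direction is not fixed.

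**6. Bounds for mean change.** Using one constant at both visits does not bracket the truth. At LLOQ 20, setting all censored values to the LLOQ gives −9.2 and setting all to 0 gives −18.7; the true value is −19.2. Opposite extremes do bracket it: −20.7 to −18.1 at LLOQ 5, −23.5 to −13.5 at LLOQ 10, and −28.7 to +0.8 at LLOQ 20. The width is LLOQ × (f_base + f_post), for example 10 × (0.161 + 0.839) = 10.0 at LLOQ 10.

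**The case against.** The rule is prespecified and disclosed, and its bias works against the drug. Nothing is tested, so no error rate is affected. Median and quartiles are already planned, individual values will be plotted, and each censored result will be listed, so a pile-up at the limit could be noticed. Table shells are a separate document and may already show counts. The larger effects need an oestradiol LLOQ of 10 to 20 pg/mL, and 20 is the responder cut-off itself. With a sensitive assay the effect is negligible.

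Most of this stands and limits the importance of the point. It does not remove it. Plots and listings do not correct a tabulated mean change, and the median change is distorted as well (step 3). Neither the SAP nor the protocol states the LLOQ that would show which case applies.

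A reader might also infer more than the documents support:

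- *That the SDs of the change endpoints are falsely small, so results look too precise.* Only visit-level SDs are certain to shrink; the SD of change can rise (step 5). SAP 5.7.3.2 plans confidence intervals only for proportions, so none rests on these SDs.
- *That all hormone endpoints are affected.* Stimulated peak LH change is practically untouched, and peak FSH is probably little affected, though that is an assumption.
- *That the primary result is at risk.* A censored value set to the LLOQ is still classed correctly while the LLOQ is at or below 3 IU/L for LH, 20 pg/mL for oestradiol or 0.3 ng/mL for testosterone.

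**Conclusion.** The point holds for the change summaries of basal LH, basal FSH, oestradiol and testosterone. Too-high on-treatment means, too-small visit-level SDs and exact-zero changes for children below the limit at both visits follow from the rule itself wherever censoring occurs. An understated mean fall also requires heavier censoring on treatment than at baseline, which suppression makes likely.

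The size cannot be fixed from the documents. Under the assumed oestradiol levels in step 3 the understatement runs from practically nothing at LLOQ 2, through 5% at LLOQ 5 (0.92/19.16), to about half at LLOQ 20 (9.95/19.16 = 52%). For basal LH, under the levels tried, it stays below 4%. The bias is conservative and leaves the primary and proportion endpoints alone under the cut-off condition above. This is a reporting weakness in secondary endpoints. It is worth correcting because the correction is cheap, and it gives no reason to doubt the primary analysis.

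**What to change.** Amend SAP 5.1 and 5.7.3.2 for basal LH, basal FSH, oestradiol and testosterone, and let 5.9.1 follow:

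1. State the central assay's LLOQ for each analyte. Tabulate n (%) below it at each visit, and the number of children below it at both baseline and that visit.
2. Print visit-level minimum, median and quartiles as below the LLOQ whenever they fall among censored values.
3. Keep the LLOQ-substituted summary and add a sensitivity range for mean change. Lower bound: censored on-treatment values at 0 and censored baseline values at the LLOQ. Upper bound: censored on-treatment values at the LLOQ and censored baseline values at 0. Do not use the same constant at both visits as a bound.

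Replacing the LLOQ by half the LLOQ would not be enough, because the exact zeros remain.

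The cost is SAP wording and a slightly longer table, from data already collected and with no effect on participants. The bounds will be wide if censoring is heavy, which is itself useful to show.
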